6.4 Assessment of feasibility

Nine months after recruitment opens accrual will be reviewed by the TSC to determine whether the feasibility criteria have been met. The feasibility criteria will be agreed in advance by the TSC but are likely to include:

- If recruitment is below 80% of target at 9 months, effective and realistic strategies to increase recruitment and retention will be required in order for the study to proceed.
- If the study does proceed, there will be an additional assessment of recruitment.
- If the number of completed follow-up participants is below 50%, the study will be stopped.

The data monitoring committee will examine unblinded safety data to determine the on-going safety profile of gentamicin and can make recommendations about trial progression to the trial steering committee.

7 RANDOMISATION AND BLINDING

7.1 Randomisation

Participants will be assigned to treatment groups using a remote internet based randomisation system maintained by the Nottingham Clinical Trials Unit (NCTU). Access to the system will be granted by the NCTU in accordance with the responsibilities on the delegation log.

Once a patient has provided consent for trial participation an authorised member of the research team will log in to the secure randomisation system and register/randomise the participant. This will generate a prescription for "trial treatment" (the actual treatment will not be specified on this prescription), containing the participant's Trial Identification Number and a unique study drug identification code for the participant. This study drug identification code will be provided to the member of staff administering the study drug to the participant who will not be blinded to the treatment allocation.

The member of staff administering the study drug will log into a separate area of the randomisation system and enter the unique study drug identification code which will reveal the treatment (gentamicin or ceftriaxone) that the participant is to receive.

This two-step approach will maintain the blinding for members of the research team who may be involved in the assessment of the participant.

7.1.1 Randomisation schedule

The randomisation schedule is based on a computer generated pseudo-random code using random permuted blocks of randomly varying size, created by the Nottingham Clinical Trials Unit (NCTU) in accordance with their standard operating procedure (SOP) and held on a secure University of Nottingham server. The randomisation will be stratified by clinical centre.

The randomisation website will be accessed by means of a remote, internet-based randomisation system developed and maintained by the NCTU.

7.2 Blinding

Only the nurse/doctor administering the treatment will know what treatment the participant has been randomised to. The participant and staff involved in the care and assessment of the participant will not know what treatment they have been randomised to. This should ensure the minimisation of any bias in assessment due to knowledge of the treatment administered,

7.2.1 Maintenance of blinding

The study drugs are taken from routine clinic stock, therefore in order to maintain blinding, the study drug must be made up (see Section 8) in an area where the participants and staff involved in the care and assessment of the participant cannot see, and all packaging must be kept out of sight.

Members of the research team, and in particular the clinician who assesses the participant at their 2 week visit, should not have any knowledge of the treatment the participant has received to allow their assessment to be conducted in an unbiased manner.

The member of staff who administers the treatment will be unblinded and should not be involved in the assessment of participants.

Each site will have a procedure to ensure blinding within the trial.

The clinician who assesses the participant at their 2 week visit should not have any knowledge of the treatment the participant has received to allow their assessment to be conducted in an unbiased manner.

7.2.2 Unblinding

To maintain the overall quality and legitimacy of the clinical trial, blind break should only occur in exceptional circumstances when knowledge of the actual treatment is absolutely essential for further management of the patient. Investigators are encouraged to discuss with the Chief Investigator if he/she believes that unblinding is necessary.

It is unlikely that individual treatment allocations will have to be prematurely disclosed since the intervention is a single dose and there is no antidote to the intervention. However, there will be an electronic web-based system available 24 hours a day where authorised personnel are able to log in to determine what treatment a participant has received. This system will record who has broken the blind, when and for what reason. If emergency unblinding is deemed to be necessary, this system should be used.

The Investigator is encouraged to maintain the blind as far as possible.

If required, the data monitoring committee will review unblinded data to determine on-going safety and tolerability of the treatments.

8 STUDY TREATMENT

8.1 Treatment Arms

There are two treatment arms within the study:

- Gentamicin (240mg) administered as a single intramuscular injection.
- Ceftriaxone (500mg) administered as a single intramuscular injection.

Both groups will also receive azithromycin (1g) administered orally.

8.2 Control Group

The control group will be the group randomised to receive ceftriaxone. Both groups will also receive standard treatment with oral azithromycin (1g)

8.3 Description of Study IMP(s)

All treatments will use standard clinic stock. Any licensed brand may be used.

Gentamicin injection (gentamicin sulphate Ph Eur equivalent to 80mg/2ml Gentamicin base).

Ceftriaxone powder for solution for injection.

Azithromycin and the lidocaine used in the preparation of the ceftriaxone injection are not considered to be IMPs.

8.4 Preparation, Dosage and Administration

Participants will be randomised to receive either a single intramuscular injection (IM) of gentamicin (240mg) OR single IM injection of ceftriaxone (500mg). Additionally both groups will receive a single oral dose of azithromycin (1g).

The injections will be prepared, following the instructions in the relevant Summary of Product Characteristics (SMPC) by an unblinded nurse.

Ceftriaxone should be dissolved in 1% Lidocaine Injection BP according to the SMPC. The solution should be administered by deep intramuscular injection.

Gentamicin should be administered by deep intramuscular injection according to the SMPC.

Treatment should be given in clinic as soon as possible after randomisation.

The batch number(s) and manufacturer(s) of all the products administered and the date of administration should be recorded on the form provided through the electronic randomisation system.

8.5 Dose Modification

No dose modifications are expected in this trial.

8.6 Dispensing and IMP accountability

An authorised, unblinded member of staff will log onto the randomisation system to determine what treatment has been allocated to the participant.

The treatment(s) will then be collected from a secure storage area and will be prepared out of sight of both the participant and any blinded members of the research team. This will minimise the potential for unblinding of the study drug

The batch numbers, manufacturers and date of administration of all products administered will be recorded on forms provided by the electronic randomisation system.

There will be no requirements for IMP accountability logs since the treatments are taken from clinic stock and batch numbers are being recorded.

8.7 Selection and Timing of dose

Gentamicin will be administered as a single IM injection (240mg) and ceftriaxone will be administered as a single IM injection (500mg). Azithromycin will be provided as a single oral dose (1g). The order of administration will be according to local protocol or participant preference.

8.8 Prior and Concomitant Therapy

Participants should not be currently receiving or have received gentamicin or ceftriaxone within 28 days of randomisation.

Participants currently receiving medication which is contraindicated for use with gentamicin, ceftriaxone, azithromycin or lidocaine, should not be included in the study.

8.9 Continuation of treatment or therapy

Study treatment is given only on one occasion. There is no requirement for any additional study treatment. If results show that the participant still has gonorrhoea, they will be offered further investigation and treatment according to local guidelines. This will not be considered part of the study.

9 PROCEDURES AND ASSESSMENTS

9.1 Overview

A summary of trial assessments is shown in Table 1 below.

Table 1. Table of assessments

	Pre-trial ¹	Baseline	End of study (2 weeks)
		Visit 1	Visit 2
Before trial (routine care – not part of trial)			
NAAT swabs	X		
Microscopy swab	X ²		
Patients with a positive diagnosis given information about trial		Х	
Trial			
Informed consent		X	
Baseline information (demography, eligibility)		X	
Pregnancy test (females)		X	
Symptom assessment		X	Х
Sexual history		X	Х
NAAT swabs		X ^{3,4}	X ⁵
Microscopy and culture swabs		X ⁴	X ⁵
Blood sample for creatinine and immune response measurement		Х	Х
Randomisation		Х	
Administration of treatment		Х	
VAS score for injection site pain		Х	Х
Optional blood sample for pharmacokinetic measures		X ⁶	
Health Utility questions			Х
Side effects/toxicity questions ⁷			Х
Collection of adverse events			Х
Serious adverse events			Х

¹Pre-trial will be the same day as Visit 1 for symptomatic patients and approx. 2 weeks before Visit 1 for asymptomatic patients.

- Heterosexual men NAAT from urethra (or urine); culture from urethra
- Men who have sex with men NAAT from urethra (or urine), pharynx and rectum. Culture from urethra, pharynx and rectum.
- Women NAAT from vagina, pharynx and rectum. Culture from cervix, pharynx and rectum.

²Only for symptomatic patients

³ Duplicate swabs required for patients in the centres which do not perform Aptima Combo NAAT testing.

⁴To complete full test screen.

⁵Only from previously infected sites

⁶30 mins after injection

⁷Questionnaire specific to known side effects

9.2 Pre-trial

Prior to being considered for entry into the trial, potential participants will undergo any diagnostics assessments in accordance with routine local clinical practice.

Routine local procedure is usually as follows:

Symptomatic patients

If the patient is symptomatic, a sample is taken for immediate microscopy and gonorrhoea NAAT from sites at risk of infection based on the patient's sexual history (urethra [or urine for men], cervix, pharynx, rectum), according to local practice. Where clinically indicated, microscopy is also performed on samples from the urethra and/or cervix (and optionally from the rectum following proctoscopy).

Symptomatic patients will be asked to wait in clinic for the results of their microscopy.

Asymptomatic patients

If the patient is asymptomatic samples are usually taken for gonorrhoea NAAT from sites at risk of infection according to local practice. No sample is required for immediate microscopy.

Asymptomatic patients will be contacted if they have a positive NAAT test result, and asked to return to clinic after their positive test results are available.

9.3.1 Pregnancy test

A pregnancy test must be performed for female patients of child bearing potential where there is a risk that they could be pregnant. Any patients with a positive pregnancy test will be excluded from entering the trial.

9.3.2 Collection of baseline information, sexual history and symptom assessment

Baseline and sexual history information will be taken from the patient and their symptoms assessed during visit 1.

9.3.3 Swabs

In all centres, participants will have additional swabs taken, if required, so that a full sampling profile is obtained for both NAAT and culture. The routine swabs taken pre-trial will contribute to the full sampling profile ie swabs are only required from those sites from which samples have not already been taken prior to entry into the trial. All samples will be analysed locally.

A full sampling profile is defined as

- Heterosexual men NAAT and culture testing from urethra (for NAAT a urine sample can be taken as an alternative to urethra)
- Men who have sex with men NAAT and culture testing from urethra, pharynx and rectum (for NAAT a urine sample can be taken as an alternative to urethra)
- Women NAAT and culture testing from cervix, pharynx and rectum (for NAAT a vaginal sample can be taken as an alternative to cervix).

Asymptomatic patients only: Participants will undergo the same study procedures as the symptomatic patients after diagnosis with the exception that a full sampling profile for NAAT and culture for the local lab will be taken ie the routine swabs taken for diagnosis (at the pretrial visit) will be taken again, in addition to the swabs required to make up the full sampling profile. This will indicate if there has been further infection since initial testing.

In centres which do not perform Aptima Combo (AC) NAAT testing, in addition to the swabs for local testing and culture, a separate full sampling profile will be taken post-randomisation for AC NAAT testing at a central laboratory (Sexually Transmitted Bacteria Reference Unit (STBRU), Public Health England).

Where possible, swabs should be taken in the following sequence: swabs for AC NAAT, swabs for BD NAAT (where applicable), swabs for culture.

9.3.4 Blood sample for creatinine and immune response measurement

If a blood sample for routine STI screening has not already been taken, two additional blood samples will be taken when it is - an extra 2-3ml to have the creatinine level measured, and 28mls for storage to measure the immune response to gonorrhoea infection (20mls serum plus 8mls EDTA). If the routine blood sample has been taken prior to informed consent, then an additional venepuncture will be performed to collect samples for baseline creatinine level and to measure immune response.

9.3.5 Randomisation and administration of treatment

The participant will then be randomised to receive either a single IM injection of gentamicin or a single IM injection of ceftriaxone. They will also receive an oral dose of azithromycin. See section 7 for further details on randomising a patient.

9.3.6 VAS score for injection site pain

The participant will be asked to assess the discomfort associated with their injection using a visual analogue scale (VAS).

9.3.7 Optional blood sample for pharmacokinetic sub-study

If the participant had consented to provide an additional blood sample for further investigation including pharmacokinetic assessment, a 10ml clotted blood sample will be taken 30 minutes after their injection.

9.4 Follow-up (Visit 2)

All participants would be asked to return to clinic a minimum of 2 weeks after treatment.

All participants will have swabs taken for NAAT and culture from all previously infected sites. In addition, swabs from the urethra and cervix will be taken for microscopy, if they were previously infected.

In addition, in centres which do not perform AC NAAT, swabs will be taken from all previously infected sites for AC NAAT at the STBRU. These swabs are additional to those taken for local NAAT testing.

Participants will have their symptoms assessed and sexual history since their last visit recorded. They will also be asked about specific known side effects and whether they have experienced any other adverse events. They will also be asked some short questions about any additional health resource use. Participants will be asked to complete a VAS indicating the pain they experienced from their previous injection.

Participants will have a 2-3ml blood sample taken for creatinine measurement and blood sampling for storage to measure immune response to gonorrhoea infection (28ml - 20ml serum plus 8ml EDTA).

Participants will be given the results of the microscopy in accordance with standard local practice and therefore they will be aware of whether their gonorrhoea has been cleared.

This would denote the end of the trial for the participant.

9.5 Sample analysis, storage and transport.

Details of sample analysis, storage and transport are provided in the trial manual.

10 CLINICAL AND LABORATORY ASSESSMENTS

10.1 Clinical Assessments

Clinical assessments - baseline

Participants will have their symptoms assessed at baseline.

Clinical assessments - follow-up

Participants will have their symptoms assessed at the 2 week follow-up visit.

They will also be asked about any side effects and adverse events, and about health resource use.

10.2 Laboratory assessments

Table 2 provides a summary of the laboratory samples to be taken.

Table 2 Laboratory samples

Table 2 Laboratory samples	Symptomatic	Asymptomatic	All	
	Visit 1	Visit 1	Visit 2	
PRE-TRIAL				
Routine swabs for microscopy	✓			
Routine swabs for local NAAT	✓	✓		
Routine swabs for local culture	✓	✓		
AFTER CO	ONSENT			
Swabs				
Additional swabs to make up full sampling	✓			
profile for local NAAT				
Additional swabs to make up full sampling	✓			
profile for local culture				
Full sampling profile for local NAAT		✓		
Full sampling profile for local culture		✓		
Full sampling profile for AC NAAT at STBRU	✓	✓		
(for centres who do not perform AC NAAT)				
Swabs from infected sites for microscopy			✓	
Swabs from infected sites for NAAT			✓	
Swabs from infected sites for local culture			✓	
Swabs from infected sites for AC NAAT at			\checkmark	
STBRU (for centres who do not perform AC				
NAAT)				
Blood				
2-3ml for creatinine levels	√	√	✓	
28ml for storage for immune study	✓	✓	✓	
10ml for pharmacokinetic analysis (optional)	✓	✓		

Routine samples should be analysed in local laboratories according to local practice.

The clinical management of the participant will be based on the results of local laboratory testing.

Additional samples to make up the full sampling profile for local NAAT and local culture will be analysed in local laboratories according to local practice.

For centres who do not perform AC NAAT, additional samples must be shipped to STBRU using materials provided by STBRU. Details instructions are provided in the Trial Manual.

For all centres, any positive cultures must be shipped to STBRU using materials provided by STBRU. Detailed instructions are provided in the Trial Manual.

Blood samples taken for the immune response study and any blood samples taken for the optional pharmacokinetic study will be sent to the University of Birmingham for preparation, storage and analyses. Detailed instructions are provided in the Trial Manual.

The results of testing by the STBRU will be transferred directly to the NCTU. Participating centres will not be provided with copies of these results.

Full details of the laboratory assessments will be provided in the trial laboratory manual. This will include details of sample preparation, storage and transfer requirements.

11 Assessment of Efficacy

Efficacy will be measured primarily by clearance of *N. gonorrhoeae* at the infected site(s), two weeks post-treatment. Clearance will be defined as a negative NAAT (Aptima Combo) at all infected sites.

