4.4 Primary and Secondary Outcome Measures

Primary outcome measure.

The primary outcome measure is clearance of *N. gonorrhoeae* at all infected sites confirmed by a negative NAAT, two weeks post treatment (as recommended by the British Association for Sexual Health and HIV). The results from the AC NAAT will be considered primary.

Secondary outcome measures

Secondary outcomes are

- clinical resolution of symptoms
- frequency of nausea/vomiting, hearing loss, dizziness and rash.
- frequency of other adverse events
- tolerability of therapy
- relationship between clinical effectiveness and MIC to inhibit N. gonorrhoeae growth
- cost effectiveness

The NAAT is an automated laboratory test and therefore it is not subject to bias through knowledge of treatment allocation. The method of NAAT performed varies between centres, therefore for those centres where the AC NAAT method is not used by the local laboratory, additional swabs will be taken and sent for testing at a central laboratory using this method. This will ensure consistency in diagnosis and response for all participants for the ascertaining the primary end point of the study.

A doctor/nurse independent of the trial will administer the study drug and will therefore not be blinded to the treatment allocation. The participant and the physicians/nurses performing the initial and follow up assessment 2 weeks after treatment, and the laboratory staff performing microbiology analyses will be blinded to the treatment given in order to minimise any bias in the collection of outcome data.

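### At centres without Aptima Combo, section 10.2 gives no route for telling the clinic about a visit 2 positive at STBRU that all local tests missed (minor patient-safety point)

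*Protocol*

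**What the plan says.** Protocol section 4.4 makes AC the deciding test for the primary outcome: "The results from the AC NAAT will be considered primary". Section 11 defines clearance in the same terms, as AC-negative at every infected site.

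Section 9.4 sets out the visit 2 sampling. For everyone: "All participants will have swabs taken for NAAT and culture from all previously infected sites". In addition, "in centres which do not perform AC NAAT, swabs will be taken from all previously infected sites for AC NAAT at the STBRU", and "These swabs are additional to those taken for local NAAT testing". Microscopy is added where the urethra or cervix was infected. The section closes the participant's involvement at that visit: "This would denote the end of the trial for the participant".

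Section 10.2 decides which results guide care: "The clinical management of the participant will be based on the results of local laboratory testing". On the central results it says: "The results of testing by the STBRU will be transferred directly to the NCTU. Participating centres will not be provided with copies of these results". It sends further detail elsewhere: "Full details of the laboratory assessments will be provided in the trial laboratory manual".

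Sections 4.1 and 8.9 provide for further investigation and treatment under local guidelines if results show persisting gonorrhoea. Neither says which results are meant. Section 6.2 has the investigator pass relevant new information to the participant.

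**The concern.** At a centre that runs AC locally, the clinic itself holds the result that decides the primary outcome. At a centre that does not, the same result exists only at STBRU and the NCTU. If it is positive while local NAAT, culture and any microscopy are all negative, the trial records a treatment failure and the clinic sees a cleared patient. The only difference between the two participants is which laboratory ran the test.

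What is at stake is a possible persisting, transmissible infection after trial treatment. Section 1 notes that there are no efficacy data for gentamicin in the pharynx or rectum, where antibiotics sometimes work less well. Visit 2 microscopy covers only the urethra and cervix, so it offers no second check at those two sites.

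**Working it through.** **1. Does any other section supply a route?**

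| Protocol section | What it provides | Does it reach an STBRU-only positive? |
|---|---|---|
| 4.1 and 8.9 | Further investigation and treatment if results show persisting infection | No: the clinic does not receive the STBRU result |
| 6.2 | Investigator passes on relevant information | No: the investigator does not hold it |
| 9.4 | Local NAAT and culture at all previously infected sites; microscopy for urethra and cervix | Only if a local test is also positive |
| 10.2 | STBRU results go to the NCTU, with no copies to centres | No exception stated for visit 2 |

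What remains is true discordance: AC-positive at STBRU and negative on every local test, at a centre without AC. A missing or invalid local result is visible to the clinic and is not part of this point.

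**2. The plan's own sample size (context only).** Section 14.1 gives 96% clearance, a 5-point margin, one-sided significance level 0.025 and 90% power.

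n per group = (1.960 + 1.282)² × 2 × 0.96 × 0.04 / 0.05² ≈ 323, so 646 in total. Allowing for 10% loss, 646 / 0.90 ≈ 718, rounded up to 720. This agrees with the protocol.

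**3. How many participants might be affected?**

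Number affected = AC failures × share at non-AC centres × share of failures negative on every local test.

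The last two inputs are not in the protocol. Assumed ranges: 25–75% of participants at non-AC centres (middle 50%), and 0–10% of AC failures locally negative throughout (middle 5%).

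- *Both arms at 96% clearance.* AC failures = 646 × 0.04 = 25.84.
  - Lower bound: 0
  - Middle: 25.84 × 0.50 × 0.05 = 0.65
  - Upper: 25.84 × 0.75 × 0.10 = 1.94
- *Gentamicin at 91% (96% less the margin), ceftriaxone at 96%.* AC failures = 323 × 0.09 + 323 × 0.04 = 29.07 + 12.92 = 41.99.
  - Lower bound: 0
  - Middle: 41.99 × 0.50 × 0.05 = 1.05
  - Upper: 41.99 × 0.75 × 0.10 = 3.15

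At centres that run AC locally the number is zero by construction.

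**The case against.** The strongest reply is that this is a deliberate and coherent design. Section 10.2 bases care on local results, and section 4.4 explains that central AC testing is there to make the endpoint consistent across centres. Every participant has local NAAT and culture at visit 2. The protocol does not claim that AC is more accurate than the local assays, so a discordant positive may be false. The trial and laboratory manuals, which are not at hand, may already contain an alert. Section 10.2 rules out sending copies; it does not expressly forbid a safety notification.

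Much of this stands. Local management is a legitimate choice and should remain, most failures will be found locally, and the manuals may settle the matter. What does not fall away is that section 10.2, followed as written, leaves the clinic uninformed, and the provisions in sections 4.1, 6.2 and 8.9 cannot act on a result that the clinic does not have.

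A reader might go further and infer that the trial knowingly leaves infected participants untreated. The documents do not support that. Both arms receive trial treatment, local testing is repeated, and nothing shows that any discordant participant will exist or would be truly infected. Nor is the primary result biased: the AC result is used as defined whether or not the clinic hears of it.

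**Conclusion.** The point holds as a minor patient-safety improvement of low severity. The textual finding is firm: the protocol states no exception and no notification route for a visit 2 STBRU positive. The size is not firm. About 0 to 3 participants in the whole trial, and roughly one or fewer at the middle values, rests on an assumed share of non-AC centres and an assumed discordance rate. The true number may be zero. Whether the gap exists in practice also depends on manuals that are not shown.

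**What to change.** Keep local management, and keep the no-copies rule for visit 1. Add to section 10.2:

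> *Once a participant's visit 2 assessments are complete, the NCTU or STBRU will notify the site of a positive visit 2 AC result when it becomes available, without disclosing treatment allocation; where local tests were negative, the site will review the participant (for example by repeat test) under local guidelines.*

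The timing is tied to the result becoming available because the protocol states no STBRU turnaround. If the trial manual already contains such an alert, a cross-reference in section 10.2 is enough.

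The cost is minor administration at the NCTU or STBRU, some notifications of positives that the site already knows about, and an occasional recall for a false positive. No trial sample, trial visit or analysis is added. The notification follows the participant's last trial assessment and does not reveal allocation, so blinding and the primary outcome are untouched.
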